This study will evaluate the changes in respiratory mechanics following TBI and determine the effect of inhaled nitric oxide on gas exchange.

4. Purpose of Study:

[figure not shown]
To determine the changes in respiratory mechanics in patients with traumatic brain injury (within 36 hours of admission and day 3 following admission).

To evaluate the effect of inhaled nitric oxide on gas exchange in patients with traumatic brain injury within 36 hours of admission.

Hypothesis: Inhaled nitric oxide improves oxygenation and reduces deadspace to tidal volume ratio following TBI.

5. Background:

Intubation and mechanical ventilation are common treatments in the care of patients with traumatic brain injury (TBI). Intubation allows for airway control and facilitates removal of respiratory secretions. Mechanical ventilation allows control of arterial carbon dioxide to aid in control of intracranial pressure. Recent evidence suggests that lung protective ventilation (tidal volumes of 6 ml/kg of predicted body weight and moderate positive end expiratory pressure) improves outcomes following brain injury and reduces brain-lung cross talk. Figure 1.

Respiratory failure following traumatic brain injury is a common complication resulting in hypoxemia and is associated with release of inflammatory mediators which may damage distal organs including the brain. The etiology of respiratory

failure following brain injury is multifactorial. Isolated head trauma is associated with neurogenic pulmonary edema and changes in ventilation perfusion matching. Concomitant trauma to the chest and pulmonary contusion may further worsen lung injury. It has been suggested that brain injury primes the lung to be a greater risk to a second hit (pneumonia, ventilator induced lung injury, lung contusion). Loss of consciousness can lead to aspiration of oral or gastric contents leading to pneumonia. Importantly, respiratory failure following TBI is implicated in 50% of deaths and prolonged ICU and hospital stay. (4,5)

The treatment of respiratory failure in TBI must balance the need to improve lung function with the negative consequences of increased intrathoracic pressure on mean arterial pressure, intracranial pressure and venous return. Traditional treatment of increasing PEEP and mean airway pressure then, represent competing interests. Methods for improving arterial oxygenation while avoiding negative hemodynamic effects are needed.

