All subjects \geq 18 years of age, admitted to the University of Cincinnati Medical Center with traumatic head injury requiring mechanical ventilation within 24 hours of admission will be screened for enrollment.

Following informed consent, patients will have assessments of respiratory function accomplished using the existing monitors within the mechanical ventilator. The NM3 respiratory monitor and airway sensor will be placed for continuous recording of data. Within 36 hours of admission, the following measurements will be made by the study staff:

1. Static and dynamic lung compliance using tidal volume and airway pressures ($CL_{static} = P_{plat} - P_{PEEP}/VT$) $CL_{dynamic} = P_{plat} - P_{PEEP}/VT$). These measurements are made non-invasively using the integral monitoring of the mechanical ventilator.
2. Airway resistance using airway pressures and flow ($Raw = P_{plat} - P_{PEEP}/Mid Expiratory flow$). These measurements are made non-invasively using the integral monitoring of the mechanical ventilator.
3. Dead space to tidal volume ratio (V_d/V_t) will be calculated using the Enghoff modification of the Bohr equation: $V_d/V_t = PaCO_2 - PeCO_2/PaCO_2$, where V_d is the dead space volume and V_t is the tidal volume; $PaCO_2$ is the partial pressure of carbon dioxide in the arterial blood, and $PeCO_2$ is the mixed expired partial pressure of carbon dioxide in the expired (exhaled) air. In the absence of arterial blood gases we will calculate $PaCO_2$ from determination of alveolar concentrations ($PaCO_2$) in expired gas.
4. Functional residual capacity (FRC) will be measured by the automated system within the GE Carestation ventilator, which uses a step change in FIO_2 to measure FRC through nitrogen washout while monitoring oxygen consumption and carbon dioxide production. These measurements are made non-invasively using the integral monitoring of the mechanical ventilator.

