5. Positive end expiratory pressure (PEEP) will be titrated from baseline PEEP as set at time of enrollment to 15 cm H_2O (in 5-cm H_2O increments) while measuring all the variables listed in #1-4 above. This method will determine the best PEEP and determine recruitability of the lung. FRC will be measured at three levels of PEEP from baseline to a maximum of 15 cm H_2O . This is an automated measurement requiring approximately 15 minutes to complete. If the patient develops hypotension (systolic pressure < 90 mm Hg or mean arterial pressure < 60 mm Hg) participation in the PEEP trial will be terminated.
6. Following these initial measurements, patients will be randomized to receive either a placebo (nitrogen and oxygen) or inhaled NO at 20 ppm for 2 hours \pm 30 minutes. After receiving the placebo or inhaled NO, the measurements in #1-4 will be reassessed (no change in PEEP will be made during this time unless required for clinical purposes).
7. If the patient remains on the ventilator at day 3 (72 hours after admission), 1-6 above will be repeated.

Subjects will receive placebo or drug for no more than 5 hours total.

If the patient responds to NO with a brisk increase in SpO₂ or PaO₂ – sudden withdrawal of NO can result in a fall in oxygenation (rebound pulmonary hypertension). This is uncommon in the absence of pulmonary hypertension. Prevention of rebound pulmonary hypertension is accomplished by increasing FIO₂ by 10-20% prior to discontinuation of NO, followed by a return to baseline FIO₂ over 30 mins.

If ICP goes up by >20% NO will be discontinued.

7. Research data collection/study procedures:

The patient baseline demographics including injury mechanism, severity and distribution, Glasgow coma scale score, age, gender, any witnessed aspiration, and lung mechanics measurements listed above will be collected to data sheets and then entered into a RedCap database. We will also record ventilator settings, lung compliance, airways resistance, dead space to tidal volume ratio, functional residual capacity, blood gases and duration of total mechanical ventilation, days in the ICU, hospital days and survival will be collected from the medical record and also entered into the RedCap database. See sequence of events for study measures.

8. Specimen collection:

The following blood samples will be taken:

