Research personnel will remain at the bedside throughout the measurements of respiratory mechanics which will require approximately 30 minutes to complete.

11. Data Safety monitoring plan and/or DSMB:

[name] will act as medical monitor for the study. He will review subjects' research data and adverse events to ensure patient safety. The medical

monitor will have the power to temporarily or permanently halt enrollment if it is deemed that patient safety is compromised.

12. Data Analysis:

Descriptive statistics will be employed to summarize relevant patient demographic factors as well as on baseline measurement of clinical variables. As a check on the success of randomization, these variables will be compared between groups using t-tests or chi-square tests, as appropriate.

The primary endpoint for this study is a change in $\text{PaO}_2:\text{FiO}_2$ ratio of 20 percent or greater between baseline and Day 3. The proportions of patients achieving success according to this criterion will be compared between groups using a two-sided z-test with pooled variance.

Group sample sizes of 19 in group one and 19 in group two achieve 82% power to detect a difference between the group proportions of 0.40. The proportion in group one (the treatment group) is assumed to be 0.10 under the null hypothesis and 0.50 under the alternative hypothesis. The proportion in group two (the control group) is 0.10. The test statistic used is the two-sided Z test with pooled variance. The significance level of the test was targeted at 0.05. The significance level actually achieved by this design is 0.0361.

Respiratory mechanics will be presented as descriptive (Mean, SD, range). Up to 43 subjects may be enrolled, in order to obtain the required 38 evaluable subjects. Patients will be removed from the study and its analysis if extubated by the clinical treatment team during the 72 hour NO protocol.

13. Data storage and confidentiality (include sample storage if applicable)

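### The airway-resistance formula divides the full end-inspiratory elastic pressure by a later, undefined 'mid' expiratory flow, so as written it does not return resistance

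*Combined protocol and SAP*

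**What the plan says.** Section 6 (Study design), item 2, introduces "Airway resistance using airway pressures and flow" and gives the formula "Raw = P_{plat} - P_{PEEP}/Mid Expiratory flow". I read it as (plateau minus PEEP) divided by mid-expiratory flow. Brackets may have been lost in text extraction, and nothing here depends on their absence.

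Item 1 of the same section pairs the same pressure difference with the full tidal volume: "CL_{static} = P_{plat} - P_{PEEP}/VT". The dynamic compliance expression uses that difference again. No formula in the plan contains peak airway pressure.

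Item 2 also states the source of the values: "These measurements are made non-invasively using the integral monitoring of the mechanical ventilator". The ventilator's algorithm is not described.

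Resistance is measured repeatedly. Item 5 measures items 1 to 4 during a PEEP titration: "Positive end expiratory pressure (PEEP) will be titrated from baseline PEEP as set at time of enrollment to 15 cm H_2O". Under item 6, after nitric oxide or placebo, "the measurements in #1-4 will be reassessed". Item 7 repeats the sequence on day 3 if the patient is still ventilated.

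The first purpose in Section 4 is "To determine the changes in respiratory mechanics in patients with traumatic brain injury". Section 12 (Data Analysis) limits the use of these data: "Respiratory mechanics will be presented as descriptive (Mean, SD, range").

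**The concern.** A resistance is the pressure driving a flow divided by that flow, both taken at the same instant. Because item 1 sets plateau minus PEEP against the full tidal volume, the plan itself treats that difference as the elastic pressure stored at end-inspiration. In passive exhalation this pressure falls as the lung empties. By mid-expiration the pressure driving flow is smaller than the numerator, so the ratio is too large.

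The word 'mid' adds a second problem. Mid-volume and mid-time are different points on the flow curve, and staff could follow the text either way.

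At stake are the level of a variable that falls under the first stated purpose and, on the mid-time reading, the meaning of its change across PEEP steps, after study gas and to day 3. Section 5 compares brain-injured patients with earlier work in which airways resistance was slightly raised, so a shifted scale would mislead such comparisons. Section 9 says the mechanics measurements will be given to the clinical team.

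**Working it through.** The plan states no numerical resistance, so there is no figure to reproduce. The check is from first principles.

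**Model (assumed).** Linear, single-compartment, passive exhalation towards set PEEP:

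- volume above the PEEP level: V(t) = V0·exp(−t/RC)
- flow: V/(RC)
- numerator of the plan's formula: Pplat − PEEP = V0/C
- let x = Te/(RC), the expiratory time in time constants

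**Mid-volume reading.** The exhaled volume is V0(1 − e^−x). When half of it has left, V0(1 + e^−x)/2 remains, so flow is V0(1 + e^−x)/(2RC). The formula returns

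(V0/C) ÷ [V0(1 + e^−x)/(2RC)] = R · 2/(1 + e^−x).

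**Mid-time reading.** At t = Te/2, flow is V0·exp(−x/2)/(RC). The formula returns R · exp(x/2) = R · exp(Te/(2RC)).

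| Te in time constants | Factor, mid-volume | Factor, mid-time |
|---|---|---|
| 2 | 1.76 | 2.7 |
| 3 | 1.90 | 4.5 |
| 4 | 1.96 | 7.4 |
| 5 | 1.99 | 12.2 |

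The mid-volume factor approaches 2 as emptying becomes complete. The mid-time factor is below 2 only when Te < 2·ln 2 = 1.39 time constants. If 'mid' meant mean flow over 25 to 75% of exhaled volume, complete emptying would give 2·ln 3 = 2.20.

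**Illustrative range.** None of these inputs is in the documents: R 10 to 15 cm H2O/L/s, C 30 to 60 mL/cm H2O, Te 2.0 to 2.5 s. The factor is 1.80 to 2.00 at mid-volume and 3.0 to 64.5 at mid-time.

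**Dependence on compliance.** True R is held at 10 cm H2O/L/s with Te = 2.0 s. The table shows what the formula would report, in cm H2O/L/s.

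| C (mL/cm H2O) | Mid-volume | Mid-time |
|---|---|---|
| 30 | 20.0 | 280 |
| 40 | 19.9 | 122 |
| 50 | 19.6 | 74 |
| 60 | 19.3 | 53 |

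At mid-volume, compliance almost cancels. At mid-time, doubling compliance from 30 to 60 cuts the reported value from 280 to 53 although resistance has not moved.

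**Check of the cause.** Start-of-expiration flow is V0/(RC). Dividing V0/C by it gives R: 10.0 for a true 10 and 15.0 for a true 15 in the simulation. The timing mismatch alone produces the error.

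**The case against.** The strongest reply is that the printed formula may not be what is applied. Item 2 says the ventilator's integral monitoring supplies the measurements, and Section 7 lists airways resistance in a sentence that also covers data taken from the medical record. If the recorded value is device output, the formula is only a loose description. This stands as a limit: a reader might infer that the reported resistance will certainly be invalid, and the documents cannot show that. It does not remove the defect, because the plan still gives this formula as its definition.

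A reader might also infer that resistance is always overstated at least two-fold. That is not supported. Two is the limit for complete, passive, linear emptying at mid-volume. Incomplete emptying gives less: 1.76 at two time constants, or 1.52 if total rather than set PEEP is used. Active breathing or a non-linear pressure-volume curve could move the factor either way. The large mid-time multiples rest on assumed inputs and on one reading of 'mid', and bedside staff would probably question a value in the hundreds.

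On the mid-volume reading, a nearly constant factor shifts the level but largely cancels in relative change. This also stands.

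Finally, the impact is limited. The Section 4 hypothesis concerns oxygenation and dead space, and Section 9 names functional residual capacity and recruitability, not resistance, when it discusses finding the best PEEP.

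**Conclusion.** The point holds as a faulty and incomplete measurement definition. The formula pairs a start-of-expiration pressure with a later flow and leaves 'mid' undefined. For passive, near-complete exhalation the overstatement is about two-fold at mid-volume. It is usually larger, and dependent on compliance, at mid-time. These sizes rest on the single-compartment model and on assumed R, C and Te; they are not estimates of the error in this trial's data.

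The effect is confined to the descriptive respiratory-mechanics results. A reader might infer that the main comparison is compromised, but the documents do not support that: the primary endpoint in Section 12 is a change in PaO2:FiO2 ratio, and resistance enters neither that endpoint nor the calculation of 19 per group. The correction is still worth making because changes in mechanics are the first stated purpose.

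**What to change.** Replace the formula in Section 6, item 2, with one in which pressure and flow refer to the same instant. For example:

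- **Inspiratory resistance:** (peak minus plateau pressure) divided by end-inspiratory flow, under constant inspiratory flow.
- **Expiratory resistance:** (plateau minus PEEP) divided by flow at the start of expiration, labelled as expiratory.
- **If a mid-volume flow is kept:** pair it with about half of (plateau minus PEEP), define 'mid' as half the exhaled volume, and note that this assumes near-complete emptying. At three time constants it returns 1.90/2 = 0.95 of R.

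State whether the recorded value is hand-calculated or the ventilator's own output; if the latter, describe the device's definition. Use one definition at baseline, at each PEEP step, after study gas and on day 3.

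The cost is one formula edit, plus confirming that the ventilator or the NM3 monitor records the pressure and flow needed. The documents do not say that either does.

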At baseline up to 3.5 ml will be taken. 1.5 ml for arterial blood gas testing (tests include: arterial pH, PaCO₂, PaO₂, SaO₂ and HCO₃) and 2 ml for measurement of inflammatory mediators specific to the lung.

After 90 to 120 minutes of nitric oxide/placebo delivery, less than 1.5 ml will be taken for arterial blood gas testing.

At the end of the study, up to 3.5 ml will be taken. 1.5 ml for arterial blood gas and 2 ml for measurement of inflammatory mediators specific to the lung.

The blood will be taken from indwelling lines when possible. If we are unable to obtain any of the blood samples, the subject will remain in the study and all other data will continue to be collected

9. Potential Benefits:

The detailed measurement of respiratory mechanics will be provided to the clinical team. This information which is not routinely measured can be used to optimize ventilator support beyond traditional monitoring. The determination of FRC and recruitability of the lung may assist the clinical team in identifying the best PEEP for each individual patient.

If the patient has a significant increase in PaO_2 associated with INO/placebo delivery, the clinical team can use that information to implement INO therapy as part of clinical care. It is unlikely that placebo will increase oxygenation appreciably. We will not unblind the study, the clinical team will have to make this decision based on a supposition of INO delivery.

Understanding the changes in respiratory function following TBI and the response to INO may improve treatment regimens for future patients.

10. Potential Risks, Discomforts, and inconveniences:

Level of risk: Greater than minimal risk.

The measurements to be made utilize non-invasive measures of lung volumes, flows, and pressures to determine mechanics.

Arterial puncture/venipuncture may cause pain/discomfort, bruising, fainting, and infection from phlebotomy sites.

Hypotension in severe pulmonary hypertension and left ventricular failure (very uncommon).

Methemoglobinemia has only been reported at 80ppm.

The stepwise increase in PEEP to determine changes in FRC will be limited to a maximum of 15 cm H_2O . PEEP can decrease venous return and cause transient hypotension. The risk of hemodynamic compromise at these low pressures is small. All subjects will have blood pressure and heart rate continuously monitored (as is standard of care) throughout the measurements.

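### Vd/Vt can be arterial-based at baseline and expired-gas-based at raised PEEP in the same patient, so a change of CO2 source alone can look like a fall in dead space

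*Combined protocol and SAP*

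**What the plan says.** Section 6, item 3 takes Vd/Vt from the Enghoff form of the Bohr equation, in which the CO2 term is arterial. It then states: "In the absence of arterial blood gases we will calculate $PaCO_2$ from determination of alveolar concentrations ($PaCO_2$) in expired gas". No formula or correction for this step is given.

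Item 5 raises PEEP from its enrolment setting to 15 cm H2O in steps of 5, "while measuring all the variables listed in #1-4 above"; Vd/Vt is item 3 of that list. Item 6 repeats the list after study gas, and item 7 repeats the whole sequence at day 3 in patients still ventilated.

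Section 8 lists arterial gases at three points: baseline, during study gas, and end of study. For the second it says: "After 90 to 120 minutes of nitric oxide/placebo delivery, less than 1.5 ml will be taken for arterial blood gas testing". It also allows for missed samples: "If we are unable to obtain any of the blood samples, the subject will remain in the study".

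Section 7 includes among the recorded data "dead space to tidal volume ratio, functional residual capacity, blood gases and duration of total mechanical ventilation". It names no field for the CO2 source and adds "See sequence of events for study measures"; that sequence is not in the supplied text.

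Section 4 puts a reduction in Vd/Vt into the hypothesis. Section 12 specifies no test for it: "Respiratory mechanics will be presented as descriptive (Mean, SD, range").

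**The concern.** Arterial and alveolar CO2 are different quantities. They differ by the arterial-alveolar gap, so Vd/Vt computed from one is not interchangeable with Vd/Vt computed from the other. Item 3 is a working rule: arterial CO2 when a gas exists, expired-gas CO2 when it does not. Combined with the sampling list in section 8, that rule can change the source between a patient's baseline and the same patient's raised-PEEP readings.

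At stake is the meaning of the Vd/Vt summaries across PEEP steps and, where a sample is missed, before and after study gas. A mean and SD that pool the two kinds of value describe neither, and a change computed across a switch mixes physiology with method.

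**Working it through.** The plan gives no figure for Vd/Vt, CO2 or the gap, so it has no figure of its own to reproduce on this point. Its power statement (19 per group, 82%) concerns PaO2:FiO2, which has no CO2 term. Exact enumeration of the pooled two-sided Z test gives power 0.8154 and alpha 0.0361, both as stated.

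**Step 1: which source applies at each reading (first session).**

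| Reading | Vd/Vt due (section 6) | Arterial gas listed (section 8) | Source under item 3 |
|---|---|---|---|
| Baseline PEEP | yes | yes | arterial |
| Raised PEEP steps | yes, item 5 | none | expired gas, unless another gas happens to exist |
| After study gas | yes, item 6 | yes, at 90 to 120 minutes | arterial, or expired gas if the sample is missed |

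This assumes that the baseline gas is drawn at baseline PEEP. With an assumed baseline PEEP of 5, 10 or 15 cm H2O, the raised steps per session number 2 (10 and 15), 1 (15) or 0. Section 8 does not say whether the baseline and 90 to 120 minute gases are repeated at day 3, so the table is not extended to that session.

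**Step 2: the effect of a switch.** Let g be the arterial-alveolar gap and suppose alveolar CO2 is used uncorrected.

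- Arterial-based (Enghoff): 1 − PeCO2/PaCO2
- Expired-gas-based: 1 − PeCO2/(PaCO2 − g)
- Drop: PeCO2 × [1/(PaCO2 − g) − 1/PaCO2]

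The drop is positive whenever g is positive.

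**Step 3: illustration.** Assumed inputs, not from the documents: PaCO2 40 and PeCO2 22 mmHg. Enghoff is 1 − 22/40 = 0.450.

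- g = 0: 1 − 22/40 = 0.450, drop 0
- g = 2: 1 − 22/38 = 0.421, drop 0.029
- g = 4: 1 − 22/36 = 0.389, drop 0.061
- g = 6: 1 − 22/34 = 0.353, drop 0.097

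With the same source at both ends of a comparison, the switch contributes 0 at any gap.

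**Step 4: where it lands.** Across PEEP steps the pattern in Step 1 can apply to every patient with a baseline gas, so the mean change is shifted by the average drop and does not average out. In the study-gas comparison, if a fraction m of patients have a baseline gas but miss the later one, the mean change is shifted by about m times the average drop. The documents give no m. The opposite pattern, with the baseline gas missed and the later one obtained, would show a false rise.

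**The case against.** The case for leaving this alone has several sound parts.

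- **Descriptive only.** No inferential result depends on Vd/Vt. This stands and limits the consequence to description and interpretation.
- **Blinding and randomisation.** Nothing links a missed gas to the arm. A reader might infer that the fallback biases the trial in favour of nitric oxide; the documents do not support that. The early comparison has arterial gases listed at both ends, and between arms a source switch is mainly noise. What remains is distortion of change from baseline within patients.
- **A correction may be intended.** Item 3 says PaCO2 will be calculated, so it cannot be taken as settled that alveolar CO2 is inserted raw. Uncorrected use is one reading, and the figures are conditional on it. The identical symbol for arterial and alveolar CO2 may be an effect of reading the PDF and is not counted as an error.
- **Unseen material.** The sequence of events or the data sheets could list extra gases or a source field. Blood gases are recorded, so the source could partly be inferred afterwards. The continuously recording airway monitor in section 6 might allow a single-source series, but its signals are not listed. These points weaken the claim without supplying a rule for comparing values.
- **Larger figures.** A drop of 0.19 can be produced from a gap of 8 mmHg, PaCO2 35 and Enghoff 0.35 (0.65 × 8/27). PeCO2 is then 22.75, and the remaining Vd/Vt is only 1 − 22.75/27 = 0.16. Because the gap is itself part of Enghoff dead space, pairing a large gap with a low total is strained, and that figure is not relied on.

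A reader might also infer that the choice of PEEP is compromised. Item 5 says the titration will identify the best PEEP, but no stated rule uses Vd/Vt to do so, and section 10 describes "The stepwise increase in PEEP to determine changes in FRC".

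**Conclusion.** The point holds as a measurement-consistency problem of moderate weight. The plan as written can set an arterial-based baseline against expired-gas values in the same patient, systematically at raised PEEP and occasionally after study gas. In the illustration this lowers Vd/Vt by 0.03 to 0.10 for gaps of 2 to 6 mmHg with no true change. These figures show possible size, not likely size.

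The conclusion rests on three conditions: alveolar CO2 is used uncorrected, the gap is positive, and the missing sequence of events adds no arterial gases at raised steps. It does not extend to the primary endpoint, the 82% power or the 38 evaluable subjects, and it is not evidence of bias between arms.

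**What to change.** Amend section 6, item 3 and section 12 to say:

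1. The CO2 source (arterial or expired gas) is recorded with each Vd/Vt value.
2. Each within-patient comparison uses one source. For example, expired-gas CO2 could be used at every PEEP step including baseline, and arterial CO2 at both ends of the study-gas comparison.
3. A stated time window matches the arterial gas to the Vd/Vt measurement. This is needed even with complete samples: delivery lasts 2 hours ± 30 minutes with measurement afterwards, while the gas is drawn at 90 to 120 minutes, so it can precede the end of delivery by up to 150 − 90 = 60 minutes.
4. Arterial-based (Enghoff) and expired-gas Vd/Vt are reported as separate variables and are not pooled. The expired-gas calculation is written out.

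The cost is a few sentences, one database field, a second Vd/Vt table with its programming, and fewer values in each summary. No extra blood samples are needed, because item 3 already provides for the expired-gas determination.

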We will ensure that paper forms are stored securely under lock and key when not in the direct custody of an investigator. Forms may have direct identifiers for the purposes of linking data from different medical records. Electronic data will not be entered with direct identifiers. A subject number will be used to link back to the identifier. The key linking identifier to subject number will not be stored with the electronic data. Electronic data will be stored in a password protected Redcap database. Analytical datasets will be stored on secure servers that also limit access to the investigator team. Should results of the study be published or reported, individual names or other identifying information will not be used. One year after the study and publication are complete the data will be destroyed.

14. Study Population

All subjects ≥ 18 and ≤ 75 years of age, admitted to the University of Cincinnati Medical Center with traumatic head injury requiring mechanical ventilation within 24 hours of admission will be screened for enrollment. Inclusion criteria will include:

1. TBI with head CT findings of injury by penetrating or blunt mechanism
2. Requiring mechanical ventilation within 24 hours of admission
3. Negative pregnancy test

Exclusion criteria will include:

1. Brain death
2. Expected survival < 48 hours
3. Pneumothorax causing chest tube to be placed
4. Elevated inspired oxygen concentration ($\text{FiO}_2 > 0.65$) on assessment
5. Hemodynamic instability (systolic BP < 100 mmHg, cardiac arrhythmias)
6. Uncontrolled ICP (>20 mmHg) necessitating bolus hypertonic saline therapy
7. Unilateral or bilateral pupil dilation and no reactive pupil
8. Spinal cord injury with hypotension
9. Severe ARDS ($\text{PaO}_2/\text{FIO}_2 < 100$)
10. Flail sternum or unilateral flail chest wall segment (2 places on ≥ 3 ribs)
11. Pulmonary contusion or lobar infiltrate visible on admission chest xray
12. Chronic lung disease with $\text{PCO}_2 > 60$ mmHg and $\text{HCO}_3^- > 32$ mmol/L
13. ICP >20 mmHg longer than 30 minutes despite hypertonic saline or mannitol therapy
14. Known heart failure (heart failure defined as EF < 20%)
15. CVP > 20 mm Hg with associated systolic blood pressure < 100 mmHg

15. Consenting process and plan

Study personnel will screen patients for inclusion and exclusion.

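### The Day 3 session (PEEP steps and study gas) is conditional only on the patient still being ventilated; the text reviewed does not re-apply the entry exclusions before it starts

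*Combined protocol and SAP*

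**What the plan says.** Section 6, item 7: "If the patient remains on the ventilator at day 3 (72 hours after admission), 1-6 above will be repeated". Items 1-6 cover the mechanics measurements, the PEEP titration to 15 cm H2O (item 5) and the blinded gas for 2 hours ± 30 minutes (item 6). A second gas session is clearly foreseen, because the exposure limit, "Subjects will receive placebo or drug for no more than 5 hours total", equals two sessions at their maximum length.

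Section 14 places its criteria at entry: patients "requiring mechanical ventilation within 24 hours of admission will be screened for enrollment". The exclusions include "Pneumothorax causing chest tube to be placed" and "Hemodynamic instability (systolic BP < 100 mmHg, cardiac arrhythmias", along with raised ICP that needs or resists treatment, and dilated pupils with no reactive pupil. In section 15, the admitting physician and ICU attending are asked to agree to enrollment, before the family is approached.

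Two stops act within a session. Item 5 ends the PEEP trial on this condition: "If the patient develops hypotension (systolic pressure < 90 mm Hg or mean arterial pressure < 60 mm Hg". After item 7 comes a rule for the gas: "If ICP goes up by >20% NO will be discontinued". Section 7 adds "See sequence of events for study measures", but that schedule is not in the text reviewed.

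**The concern.** The sponsor judged certain states unsuitable for these interventions at entry. Several can arise between enrollment (within 36 hours of admission) and 72 hours. Followed literally, item 7 would start the PEEP steps and the gas in a patient who by then has ICP above 20 mmHg despite treatment, systolic pressure of 90-99 mmHg, no reactive pupil or a new chest tube. No reason is given why a state that bars the first session is acceptable for the second. The plan also does not say whether a patient whose PEEP trial or nitric oxide was stopped in session 1 should be exposed again.

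The first stake is patient safety, in a study that section 10 rates as greater than minimal risk and that relies on surrogate consent. The second is consistency: without a written rule each bedside team decides for itself, and Day 3 exposure varies with no recorded reason, although the primary endpoint in section 12 runs from baseline to Day 3.

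**Working it through.** **1. Which exclusions can newly apply by 72 hours.** Going through section 14:
- Can change: 1 (brain death), 2 (expected survival), 3 (pneumothorax with chest tube), 4 (FiO2 > 0.65), 5 (systolic < 100 mmHg or arrhythmia), 6 (ICP > 20 mmHg needing bolus hypertonic saline), 7 (pupils), 9 (PaO2/FiO2 < 100), 13 (ICP > 20 mmHg for over 30 minutes despite treatment).
- Already covered: 15 (CVP > 20 mmHg with systolic < 100 mmHg) lies inside 5.
- The others are injury features, the admission chest film or pre-existing disease.

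**2. What the in-session stops leave open.**
- *Blood pressure.* Entry bars systolic < 100; the PEEP stop is systolic < 90 or MAP < 60, and it is written only for the PEEP trial. The gap is systolic 90-99 with MAP ≥ 60. Taking MAP = (S + 2D)/3 (an assumption), MAP < 60 requires D < (180 − S)/2. For S = 90 that is D < 45 mmHg; for S = 99 it is D < 40.5 mmHg. So in this range the MAP limit acts only at a low diastolic pressure.
- *ICP.* The rule is relative and written for nitric oxide: stop above 1.2 × starting ICP. Since 20/1.2 = 16.7, it acts below 20 mmHg for any start under 16.7, which is protective. From an illustrative start of 25 mmHg it acts only above 25 × 1.2 = 30 mmHg. It says nothing about whether a patient already at 25 should start.
- *Arrhythmia, pupils, chest tube.* No stop is written.

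**3. Exposure.** One gas session lasts 2 h ± 30 min, or 90-150 minutes; 2 × 2.5 h = 5.0 h, the stated limit. Section 10 places research staff at the bedside for the mechanics measurements, about 30 minutes.

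**4. What withholding would cost in power.** Inputs from section 12: 19 per group, control rate 0.10, treatment rate 0.50, two-sided pooled z-test at 0.05. Exact enumeration of all outcomes, rejecting when |z| ≥ 1.96, gives significance level 0.0361 (plan: 0.0361) and power 81.5% (plan: 82%), so the plan's figures are reproduced.

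Now let k of the 19 nitric oxide patients miss Day 3 gas and respond at rate r, with the rest at 0.50. The average rate is [k·r + (19 − k)·0.50]/19.

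| k | Average rate, r = 0.10 | Difference from control | Exact power, r = 0.10 | Exact power, r = 0 |
|---|---|---|---|---|
| 0 | 0.500 | 0.400 | 81.5% | 81.5% |
| 1 | 0.479 | 0.379 | 77.8% | 76.8% |
| 2 | 0.458 | 0.358 | 73.5% | 71.4% |
| 3 | 0.437 | 0.337 | 68.9% | 65.3% |

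These losses arise only if the endpoint blood gas is drawn after Day 3 gas. Section 8 lists a sample at the end of the study without placing it before or after the Day 3 gas. If it is drawn before, withholding has no effect on the endpoint.

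**The case against.** The best reply is that the absence cannot be proven. Section 7 refers to a sequence of events outside the text reviewed, and a per-session check could sit there. That stands: a reader might infer that the trial has no Day 3 check at all, and the documents do not support saying so. They support only that none appears in the text reviewed, where the schedule is cited for study measures.

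A second reply is that the session is well guarded. Both in-session stops, the 15 cm H2O ceiling and the 5-hour limit operate on Day 3. Item 6 allows PEEP changes when clinically needed, blood pressure and heart rate are monitored continuously, section 10 calls the hemodynamic risk small, and a medical monitor reviews adverse events. ICU clinicians would probably hold back an unstable patient. This limits the likely harm. It does not say who should not start, and much the same clinical setting existed at entry, where the sponsor still wrote criteria.

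Two further inferences go too far. One is that any systolic pressure below 100 mmHg would go unchecked: item 7 repeats item 5 with its stop, so the open range is 90-99 with MAP of at least 60. The other is that an entry limit stricter than a stopping limit is itself an error; it is not. The gap is the missing start rule.

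**Conclusion.** The point holds for the text reviewed and should be fixed. Item 7 makes repeat exposure to PEEP steps and study gas depend only on continued ventilation, and neither the enrollment criteria nor the in-session stops decide who should not start. Confidence is moderate because of the unseen sequence of events.

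The number of patients who would meet an exclusion at 72 hours is not given, and no estimate is offered. A reader might infer that patients are likely to be harmed; the documents do not show this. The power figures are scenarios that assume 1 to 3 withheld patients, not bounds. The blood pressure calculation rests on the usual MAP approximation. Whether the PEEP steps need their own ICP stop is a separate question and no part of this conclusion.

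**What to change.** Amend item 7 so that, immediately before the Day 3 session, staff re-check section 14 exclusions 1-7, 9 and 13 (15 needs no separate line) and whether the PEEP trial or nitric oxide was stopped in session 1. Judge the exclusions on the patient's state at that moment, so that a resolved earlier episode, such as hypertonic saline on Day 1, does not count.

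If any is met, do not start the Day 3 PEEP steps or the study gas. Still take the Day 3 blood gas and passive mechanics where possible, record the reason, and keep the patient in the randomised group for analysis. If the sequence of events already contains such a check, citing it in item 7 is enough.

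The cost is a short amendment and one checklist on the Day 3 form, using bedside values. Some patients will lack a Day 3 PEEP curve or second gas session, with the conditional power loss shown above. Keeping withheld patients in the analysis means the check need not use up any of the 43 − 38 = 5 spare enrollment places, provided the Day 3 blood gas is obtained.
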